9.3 Analysis Supporting Key Secondary Objectives

The following family of endpoints that each assess tau pathophysiology will be used to determine proof-of-concept. These endpoints will be tested together to control the family-wise error rate at the desired alpha of 0.10.

- Change in CSF pTau217 [Time frame: baseline to Week 24]
- Change in plasma pTau217 [Time frame: baseline to Week 24]
- Change in CSF total tau [Time frame: baseline to Week 24]

The estimand for these endpoints is specified as follows:

Treatment regimens:	ASN51 , ASN51 , or placebo, once daily
Population:	Early Alzheimer's Disease, as described by study inclusion / exclusion criteria (Sections 5.3 and 5.4)
	The mITT population will be used in the analysis
Endpoints	CSF pTau217, plasma pTau217, CSF total Tau
Summary statistic	Difference between treatments in mean change from baseline to Week 24
Intercurrent events	 A treatment policy strategy will be used to account for deviations in study medications and in use of concomitant medications.
	 Data as collected will be analyzed without multiple imputation via ANCOVA or MMRM as appropriate.
	 As sensitivity analyses, missing data will be multiply imputed under the missing not at random assumption using both jump to placebo (reference) based imputation and the tipping point methodologies.

ANCOVA = analysis of covariance; CSF = cerebrospinal fluid; mITT = modified Intent-to-Treat; MMRM = mixed effects model for repeated measures.

Descriptive statistics for each endpoint will be summarized for each visit where that endpoint is assessed. The ANCOVA analysis described in Section 9 will be used to assess CSF pTau217 and CSF total Tau as the endpoints are collected only once post-baseline. The MMRM analysis described in Section 9 will be used to assess plasma pTau217, which is collected repeatedly post baseline. For sensitivity analyses of the key secondary endpoints, missing data will be imputed using the multiple imputation technique under the missing not at random assumption using both placebo (reference) based imputation and the tipping point method.

Multiplicity across these 3 endpoints and 2 dose arms will be controlled in the following manner. Testing will begin with the dose using the Hochberg step up procedure. The results for these 3 endpoints will be ordered from smallest to largest p value within the arm. Significance will be based on testing the largest p value at $\alpha = 0.1$, the 2nd endpoint in the order will be tested at $\alpha/2 = 0.05$, and the 3rd endpoint will be tested at $\alpha/3 = 0.033$. If any of the 3 tests within the arm are significant, the secondary endpoint is considered met for the dose and testing will proceed to the arm using the 0.1 significance level.

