9 STATISTICAL CONSIDERATIONS

A general description of the statistical methods planned to analyze the safety and preliminary efficacy of the IMP is outlined below. The analyses specified in this protocol will be expanded in the Statistical Analysis Plan (SAP) to include a detailed description of the analyses. The SAP will be finalized and approved prior to database lock.

Trial data will be reported using summary tables, figures, and data listings. Descriptive statistics will be used to summarize the data. For continuous variables, the mean, standard deviation, median, minimum, and maximum will be provided. For discrete data, incidence and percentages will be provided. Statistical tests will be 1-sided at the alpha level of 0.10, unless stated otherwise. P-values will be used descriptively and will have no inferential value. All p-values will be reported to the 3rd decimal place. Summary tables will include the data from the ASN51 groups combined, i.e., Placebo and ASN51 for the DB and LTE periods, respectively.

Baseline for all clinical laboratory evaluations, vital signs measurements, and 12-lead ECGs will be defined as the last evaluation before IMP administration. The timing of each protocol-specified assessment is provided in the Schedules of Activities (Section 1.3).

Two sets of analyses will be conducted. The first set of analyses will be conducted after all participants have had the opportunity to complete the Week 24 assessment or have discontinued the study (primary analysis Sections 9.1 through 9.7). The second set of analyses will be conducted when all participants have had the opportunity to complete the LTE or discontinued the study (Section 9.8).

For endpoints collected only once post-baseline, changes from baseline will be analyzed using an analysis of covariance (ANCOVA) model that includes the categorical effects of APOE4 status, use of AD medication, treatment group, and the continuous covariate of the baseline value of the variable being analyzed. The one-sided p-value (t-test on least squares means at Week 24) and two-sided 80%, and 90% confidence limits will be tabulated. The model will also include the randomization stratification factors (i.e., APOE4 status and use of AD medication).

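### The printed steps of the Hochberg rule in Section 9.3 leave the smallest of the three p-values without a significance level, which contradicts the named procedure

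*Combined protocol and SAP*

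**What the plan says.** Section 9.3 makes CSF pTau217, plasma pTau217 and CSF total tau the family that determines proof-of-concept, and states: "These endpoints will be tested together to control the family-wise error rate at the desired alpha of 0.10". Section 9 sets the sidedness: "Statistical tests will be 1-sided at the alpha level of 0.10, unless stated otherwise".

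The multiplicity paragraph at the end of Section 9.3 starts with one dose (its label is redacted), "using the Hochberg step up procedure". It then gives the order: "The results for these 3 endpoints will be ordered from smallest to largest p value within the arm". The levels follow. "Significance will be based on testing the largest p value at" 0.1; then "the 2nd endpoint in the order will be tested at $\alpha/2 = 0.05"; then the 3rd endpoint gets one third of alpha, 0.033.

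The success rule, which also opens testing of the other arm at 0.1, is: "If any of the 3 tests within the arm are significant, the secondary endpoint is considered met for the dose".

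**The concern.** The ordering sentence runs upward: first is the smallest p-value, third is the largest. The levels sentence runs downward: it starts at the largest p-value, named by its size, and then uses ordinal positions. The second level is tied expressly to the stated order, so the natural reading of the third is by position too. Read that way, the largest p-value carries two levels (0.10 and 0.033) and the smallest carries none. Hochberg requires the smallest to be tested at 0.033.

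This matters because one significant test of three decides whether proof-of-concept is met for the first dose and whether the second dose is tested at all. A programmer working from the printed steps and one working from the procedure's name could reach different decisions on the same data. Settling that after unblinding would be open to challenge.

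**Working it through.** **Inputs.** Family-wise alpha 0.10 (Section 9.3); one-sided tests (Section 9); 21 completers per arm, 20% difference, 25% SD, so d = 20/25 = 0.8, and 90% power at one-sided 0.10 (Section 9.10). The documents give no correlation between the three markers; 0.2, 0.5 and 0.8 are assumed, with 0 as an arithmetic check.

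**1. The plan's own figure.** Noncentrality = 0.8 × √(21/2) = 2.592. With 40 degrees of freedom the one-sided 0.10 critical value is 1.303 and the noncentral t gives power 0.900. The normal approximation gives Φ(2.592 − 1.282) = 0.905. The stated 90% is reproduced. It is a single-endpoint figure at unadjusted 0.10 and does not depend on the point made here.

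**2. The levels.** 0.10/1 = 0.100, 0.10/2 = 0.050, 0.10/3 = 0.0333. These are the Hochberg levels, and the largest p-value is correctly placed at full alpha.

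**3. The two readings side by side.**

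| p-value | Position in the stated order | Level under Hochberg | Level counting by stated position |
|---|---|---|---|
| Smallest | 1st | 0.033 | none |
| Middle | 2nd | 0.05 | 0.05 |
| Largest | 3rd | 0.10 | 0.10 and 0.033 |

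In the right-hand column the 0.033 is redundant, because 0.10 already covers it.

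**4. Where the decisions part.** Hochberg declares the dose met if largest ≤ 0.10, or middle ≤ 0.05, or smallest ≤ 0.033. The positional reading keeps only the first two conditions. They differ exactly when smallest ≤ 0.033, middle > 0.05 and largest > 0.10.

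- p = 0.02, 0.06, 0.20: met under Hochberg (0.02 ≤ 0.033); not met by position (0.06 > 0.05, 0.20 > 0.10).
- p = 0.001, 0.20, 0.50: the same split, so the affected results need not be borderline.

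The positional conditions are a subset of Hochberg's, so that reading can only turn met into not met.

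**5. Hand check with independent markers.** Let F(a) be the probability that a marker's p-value is at most a. For a marker with no effect F(a) = a. For a responding marker F(a) = Φ(2.592 − z), with z the upper-a normal quantile: 0.776, 0.828 and 0.905 at a = 0.0333, 0.05 and 0.10. The probability that the decision changes is the sum, over which marker is smallest, of F(0.0333) × [P(both others > 0.05) − P(both others between 0.05 and 0.10)].

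- No effect: 3 × 0.0333 × (0.95² − 0.05²) = 0.090.
- All three respond: 3 × 0.776 × (0.172² − 0.077²) = 0.055.
- One responds: 0.776 × (0.95² − 0.05²) + 2 × 0.0333 × (0.172 × 0.95 − 0.077 × 0.05) = 0.698 + 0.011 = 0.709.

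Simulation at zero correlation gives 0.0895, 0.0545 and 0.7101, in agreement.

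**6. Simulation with correlated markers.** 400,000 trials per scenario, equicorrelated normal statistics, noncentrality 2.59 for each responding marker. Probability that the first dose is met, at correlation 0.2/0.5/0.8:

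| Scenario | Hochberg | Positional reading |
|---|---|---|
| No effect | 0.094/0.086/0.074 | 0.015/0.031/0.052 |
| All three respond | 0.98/0.95/0.90 | 0.92/0.89/0.87 |
| Two respond | 0.94/0.90/0.86 | 0.71/0.73/0.76 |
| One responds | about 0.78 throughout | about 0.09 throughout |

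A rerun agrees within 0.01. The 0.92 sits close to a rounding boundary: the rerun gave 0.914. In no simulated trial was the dose met by position but not under Hochberg.

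**The case against.** The best defence is that the paragraph can be read correctly. It names Hochberg, fixes the largest p-value at 0.1 by name, uses the right three levels, and speaks of three tests on three endpoints. If the third endpoint were the largest p-value again, only two endpoints would be tested and the 0.033 would do nothing. The only reading that fits the name and gives three tests puts the smallest p-value at 0.033. This stands as evidence of intent. It does not rescue the wording, because the reader must set aside the stated order to recover the rule.

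Four stronger conclusions might be inferred, and the documents do not support them:

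- **Inflated type I error.** Testing the smallest p-value at 0.10 would give a family-wise error of 0.25/0.22/0.17, but the text says in words that the largest is the one tested at 0.1. The literal reading is conservative.
- **Wrong levels.** The levels are correct; only their attachment to the stated order fails.
- **A power collapse in the planned design.** The contrast of 0.78 with 0.09 needs a single responding marker. Section 9.10 plans a 20% difference for the plasma and CSF markers alike, and there the loss is 3 to 6 points.
- **A missing step-up consequence that changes proof-of-concept.** The printed steps do not say that smaller p-values are also rejected once one passes. Taken literally, 0.06, 0.07, 0.08 makes only the weakest marker significant, where Hochberg rejects all three. But the procedure's name carries that consequence, and the dose is met either way because one significant test suffices.

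It is also fair to say that the synopsis and Section 9 call p-values descriptive and that Section 9 leaves detail to a SAP still to be finalised. That limits the regulatory weight. Section 9.3 nevertheless claims family-wise control for proof-of-concept and makes the second dose conditional on these p-values.

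**Conclusion.** Wrong as written; a wording correction only. The steps printed in Section 9.3 contradict the procedure it names, because the order ascends while the levels descend. If the printed order were followed, the error would run one way: a dose that Hochberg declares met could be called not met, and the second dose would then go untested.

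With all three markers responding as planned, the loss is 0.98 − 0.92 = 0.06, 0.95 − 0.89 = 0.06 and 0.90 − 0.87 = 0.03 at correlations 0.2, 0.5 and 0.8. With one responding marker it is about 0.78 − 0.09 = 0.69. These figures rest on 21 completers per arm, d = 0.8, a normal approximation and assumed correlations. The contradiction itself rests on none of them. The check covers the rule within the first-tested dose; error control across the two doses was not examined here.

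**What to change.** Keep the sentence that names the starting dose and Hochberg, and keep the sentence that defines success and opens the second arm. Replace only the ordering sentence and the levels sentence with:

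> Within the dose, the one-sided p-values are ordered from largest to smallest. If the largest is ≤ 0.10, all three endpoints are significant; otherwise, if the middle is ≤ 0.05, the endpoints with the middle and smallest p-values are significant; otherwise, if the smallest is ≤ 0.0333 (0.10/3), that endpoint alone is significant.

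This also states the step-up consequence. Carry the same text into the SAP before database lock. The cost is two sentences; data, sample size and design are unchanged.

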9.10 Sample Size Determination

The sample size was not derived statistically, but empirically determined based on the safety objectives of this dose ranging trial. With N = 21 per arm (accounting for a 20% dropout rate), the rule of 3 suggests that the probability of observing at least 1 occurrence of individual AEs is at least 95% if the incidence rate is greater than 1/(N/3), which is approximately 14%.

For the plasma and CSF key secondary biomarker endpoints (CSF pTau217, plasma pTau217, and CSF tTau), the study has 90% power at a one-sided alpha of 0.1 to observe a baseline-adjusted change from baseline of 20% relative to placebo assuming a 25% standard deviation (e.g., Cohen's d of 0.8). A difference of 20% from placebo has been observed for CSF tTau and pTau with the OGA inhibitor Thiamet G in the rTg4510 tau model (Wang, Smith et al. 2018) and is a similar effect size to what has documented after 24-weeks of treatment of early AD patients with amyloid lowering therapies like lecanemab and donanemab (Salloway 2023, van Dyck, Swanson et al. 2023).

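### Section 9.3 states 0.10 error control over 3 endpoints and 2 doses; it holds per dose and for the dose-level claims, but not over all six tests when only some first-dose markers move

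*Combined protocol and SAP*

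**What the plan says.** Section 9.3 names CSF pTau217, plasma pTau217 and CSF total tau as the family that decides proof of concept: "These endpoints will be tested together to control the family-wise error rate at the desired alpha of 0.10". It then widens the scope: "Multiplicity across these 3 endpoints and 2 dose arms will be controlled in the following manner".

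The rule has three parts.
- At the first dose, the three p-values go through Hochberg, with thresholds 0.10, 0.05 and 0.033 from largest to smallest.
- The gate is: "If any of the 3 tests within the arm are significant, the secondary endpoint is considered met for the dose".
- After that, "testing will proceed to the arm using the 0.1 significance level". No procedure is named for the three tests at the second dose. The dose names are blacked out, but only the fixed order matters here.

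Section 9 sets the default: "Statistical tests will be 1-sided at the alpha level of 0.10, unless stated otherwise". The sentence after it, repeated in the Section 1.1 synopsis, says: "P-values will be used descriptively and will have no inferential value". Section 9 also says: "The analyses specified in this protocol will be expanded in the Statistical Analysis Plan (SAP"), to be finalised before database lock. No such expanded plan is in the supplied text. Section 9.4.1 tests tau PET at one-sided 0.10, also in proof-of-concept terms.

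**The concern.** Three endpoints and two dose arms make six tests, and the scope sentence can fairly be read as covering all six. The gate does not support that reading. A single first-dose rejection hands the whole 0.10 to the second dose, although the first-dose markers not yet rejected have released nothing. If one marker truly moves at the first dose, it opens the gate. The first-dose markers that do not move can still produce a false rejection with probability up to 0.10, and the second dose then has another 0.10 of its own.

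At stake is what the study report may say. A statement listing every significant marker at both doses, described as controlled at 10% overall, could carry a higher error rate than stated. Separately, Section 9.3 uses p-values to declare an endpoint met under error control, while Sections 1.1 and 9 deny p-values any inferential value. A reader cannot tell which is meant.

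**Working it through.** **Inputs from the documents.** 21 completers per arm, one-sided 0.10, and "change from baseline of 20% relative to placebo assuming a 25% standard deviation" (Section 9.10), so d = 20/25 = 0.8. Allocation is 1:1:1 with one shared placebo arm (Section 4.1).

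**Inputs assumed.** Equal correlation between the three markers of 0 to 0.8 (the documents give none), and Hochberg at 0.10 at both doses.

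**Plan's own figure.** Power = Φ(d·√(n/2) − z₀.₉₀) = Φ(0.8 × √10.5 − 1.2816) = Φ(1.311) = 0.905. The noncentral t gives 0.900. The stated 90% reproduces.

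**What follows from the rule.**
1. *Dose-level claims.* If neither dose works, a false claim requires a first-dose rejection, which Hochberg holds at 0.10. If at least one first-dose marker moves, only the second-dose claim can be false, again at most 0.10.
2. *Markers within one dose.* Hochberg holds each dose at 0.10, and the gate can only lower the second dose's error.
3. *All six pooled.* Pooled error = (first-dose error) + (second-dose error) − (both). If true effects open the gate while null markers remain at the first dose, both terms can approach 0.10. The ceiling is 0.10 + 0.10 = 0.20.

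**One case in numbers.** Two first-dose markers at d = 0.8, second dose null, correlation 0.3, 26 per arm (the number randomised): the gate opens in 0.963 of trials, first-dose error is 0.098 and second-dose error 0.092. Pooled error is 0.168, so both occur together in 0.098 + 0.092 − 0.168 = 0.022.

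**Simulation at 21 per arm.** 300,000 trials per case, t-tests on 57 df (63 minus three arms, baseline and two stratification terms). Pooled six-test error with the second dose null:

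| True effect at first dose | d = 0.2 (5%) | d = 0.4 (10%) | d = 0.6 (15%) | d = 0.8 (20%) |
|---|---|---|---|---|
| One marker moves | 0.088–0.091 | 0.110–0.115 | 0.125–0.137 | 0.134–0.156 |
| Two markers move | 0.080–0.099 | 0.116–0.129 | 0.144–0.151 | 0.150–0.168 |

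- Global null: 0.072–0.099.
- All three move at the first dose (d = 0.8), none at the second: 0.074–0.098.
- Different markers move at the two doses (d = 0.8): 0.143–0.177.
- Dose-level claims: at most 0.099 in every case.
- Markers within one dose, from a separate run of 200,000 trials per case: 0.042–0.101 at the first dose and 0.031–0.099 at the second, with simulation error about 0.0007.

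The point where pooled error passes 0.10 depends on the correlation. Two markers at correlation 0.8 give 0.102 at d = 0.22; one marker gives 0.099–0.102 at d = 0.30. A separate calculation with normal statistics and correlations up to 0.9 gave 0.128–0.168 at d = 0.8.

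**The case against.** The strongest reply is that the plan needs no six-test guarantee. The family in Section 9.3 is the three listed markers, the decision it defines across doses is whether each dose is met, and both are controlled. That stands, and it limits the point. It does not rescue the scope sentence, which names three endpoints and two arms without saying that the control is per dose.

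The excess also needs disagreement among markers: one or two move, and another stays at exactly zero at the first dose. Section 9.10 plans the same 20% effect for all three, and if that is true at the first dose the pooled rate stays within 0.10. This limits how often the gap would matter. Even so, three separate tests with an any-of-three gate allow for markers that disagree.

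Three stronger readings are tempting, and the documents do not support them.
- *The proof-of-concept decision is inflated.* It is not: the dose-level claims stay within 0.10.
- *No statement about a single marker is error-controlled.* This is too broad: within either dose, the three marker claims are held at about 0.10.
- *Second-dose markers are each tested unadjusted at 0.10.* Dose-level control would then fail: a null second dose would be declared met in 0.17–0.27 of trials when all three markers move at the first dose at d = 0.8. But repeating Hochberg is the natural reading of a partly redacted sentence. The silence calls for one clarifying sentence and is not evidence of a faulty test.

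Deferral to the SAP could settle the wording, but that could not be checked in the supplied text.

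**Conclusion.** Wrong as written, in scope only. Assuming Hochberg at both doses, 0.10 holds for the two ordered dose-level claims and for the three markers within each dose. It does not hold over the six tests pooled when one or two, but not all, first-dose markers truly move: about 0.13 to 0.17 at d = 0.8 with 21 per arm and a null second dose. The excess shrinks with smaller effects and appears from about d = 0.2 to 0.3 upward.

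These figures rest on assumed marker correlations of 0 to 0.8. The simulated maxima cover the cases run and are not proven bounds. The conflict with the sentence on inferential value is textual and needs no assumption. Severity is minor to should-fix: the dose-level decision is sound under the natural reading.

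**What to change.** - In Section 9.3, state that the same Hochberg procedure at 0.10 is applied to the three endpoints at the second dose.
- Replace the scope sentence with: *the family-wise error rate is controlled at one-sided 0.10 for the two dose-level claims across doses, and for the three endpoints within each dose; it is not controlled at 0.10 over all six endpoint-by-dose tests.*
- In Section 1.1 (Statistical Methods) and Section 9, exempt the Section 9.3 tests from the sentence denying p-values inferential value, and say whether the tau PET test in Section 9.4.1 is also exempt.
- Alternatively, remove the error-control wording and treat all of these tests as descriptive.

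The cost is a few sentences, carried into the SAP before database lock. The downside is that the stated control covers a narrower set of claims than the current text suggests.

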9.4 Analysis Supporting Other Secondary Objectives

9.4.1 18F MK-6240 PET Scan

Tau burden, assessed using ¹⁸F-MK-6240 standardized uptake value ratio (SUVR), will be calculated in a volume weighted composite medial temporal region of interest (ROI), encompassing the entorhinal cortex, amygdala, parahippocampal cortex, and hippocampus (Jack, Wiste et al. 2017, Sanabria Bohorquez, Baker et al. 2024). The following family of endpoints that each assess tau pathophysiology will be used to determine proof-of-concept.

The following endpoint will be tested at the desired one-sided alpha of 0.10.

Change in SUVR in the medial temporal ROI [Time frame: baseline to Week 24]

The estimand for this endpoint is specified as follows:

Treatment regimens:	ASN51 , ASN51 , or placebo, once daily
Population:	Early Alzheimer's Disease, as described by study inclusion / exclusion criteria (Sections 5.3 and 5.4)
	The mITT population will be used in the analysis
Endpoints	Tau PET medial temporal ROI SUVR
Summary statistic	Difference between treatments in mean change from baseline to Week 24
Intercurrent events	A treatment policy strategy will be used to account for deviations in study medications and in use of concomitant medications.
	Data as collected will be analyzed without multiple imputation via ANCOVA or MMRM as appropriate.
	 As sensitivity analyses, missing data will be multiply imputed under the missing not at random assumption using both jump to placebo (reference) based imputation and the tipping point methodologies.

ANCOVA = analysis of covariance; CSF = cerebrospinal fluid; mITT = modified Intent-to-Treat; PET = positron emission tomography; ROI = region of interest; SUVR = standardized uptake value ratio.

Descriptive statistics will be summarized for each visit where that endpoint is assessed. The ANCOVA analysis described in Section 9 will be used to assess tau PET medial temporal ROI SUVR as the endpoint is collected only once post-baseline in the DB intervention period.

